### **11.3 Methods for Evaluation of Measurable Disease**

All measurements should be taken and recorded in metric notation, using a ruler, calipers, or digital measurement tool. All baseline evaluations should be performed as closely as possible to the beginning of treatment and never more than 14 days before the beginning of the treatment.

The same method of assessment and the same technique should be used to characterize each identified and reported lesion at baseline and during follow-up

CONFIDENTIAL

This document is confidential. Do not disclose or use except as authorized.

## 11.4 Confirmation of Progression

In order to distinguish potential treatment-associated pseudoprogression from progressive disease and minimize premature discontinuation of study medication, participants who initially meet radiologic criteria for disease progression within six months of starting study therapy should remain on study until confirmation of progression with an MRI performed 12 weeks later (see Section 11.2) as long as the following criteria are met:

- They are felt to be deriving clinical benefit from study therapy;
- They are tolerating study therapy without significant adverse events;
- They are not experiencing significant neurologic decline felt to be related to underlying progressive tumor and not due to co-morbid event (seizures, stroke, infection, etc) or change in concomitant medication (i.e. decrease in corticosteroid medication).

If the follow-up imaging assessment confirms that progression has occurred, the date of progression will be the date at which progression was first determined. Participants who develop significant new or worsened neurologic deficits not due to co-morbid event or change in co-administered medication at any time within the three months follow-up window will be designated as a treatment failure and should discontinue study therapy. For these participants, the date of actual tumor progression should also be back-dated to the date radiographic PD was initially identified.

If radiographic findings during the three months follow-up window meet criteria for SD, PR or CR according to RANO and there are no new or worsened neurologic deficits, such participants will be considered as deriving clinical benefit from therapy and allowed to continue treatment.

Participants who develop radiographic findings greater than six months from study therapy initiation are expected to have a low likelihood of ultimately deriving clinical benefit and should be considered a treatment failure with a recommendation to discontinue their current therapy. Confirmation of radiographic progression on follow-up imaging 12 weeks later will not be required for such patients.

[figure not shown]
Participants who satisfy criteria to confirm radiographic progression outlined above may continue to receive study therapy pending evaluation of the potential benefits and risks of study therapy by the treating investigator in consultation with the study Principal Investigator or designee. Continuation of study therapy may be considered pending follow-up imaging as long as patients are deriving apparent clinical benefit with minimal and acceptable toxicity. In contrast, clinicians may consider interrupting study therapy for participants who require a significant increase in corticosteroids (i.e. > 4 mg of dexamethasone or equivalent per day) for significant evolving symptoms associated with cerebral edema or who are experiencing more than mild treatment-related toxicity such as immune related adverse events grade  $\geq 2$ . If interrupted, study therapy may be resumed when deemed to be safe and in the best medical interest of the participant by the treating investigator in consultation with the study Principal Investigator or designee. Factors for consideration in the decision of when to resume study therapy include but are not limited to: decrease in systemic dexamethasone to  $\leq 4$  mg/day; enhancing tumor burden is classified as SD, PR or CR on follow-up scan; or when relevant treatment-related toxicity has resolved to grade  $\leq 1$  or pre-treatment baseline.

An algorithm highlighting treatment decision making for radiographic progression is provided in Figure 11.4-1.

CONFIDENTIAL

This document is confidential. Do not disclose or use except as authorized.

Figure 11.4-1 iRANO Algorithm for Treatment Decision Making for Radiographic Progression

## 11.5 Best Objective Response (BOR)

Best objective response (BOR) should be determined based on response designations recorded per iRANO defined criteria. The participant's BOR assignment will depend on the findings of both target and non-target disease and will also take into consideration the appearance of new lesions.

The assessments that will contributed to the evaluation of BOR include the response assessment recorded between the date of and the first to occur of the following:

- 1) The date of objectively documented progression per RANO criteria  
 -OR-
- 2) The date of subsequent therapy  
 -OR-
- 3) The date of pathology results from diagnostic surgical resection

Among the available response assessments, the criteria listed in Table 11.5-1 will be used to determine BOR.

CONFIDENTIAL

This document is confidential. Do not disclose or use except as authorized.

**Table 11.5-1 Assessment of Best Overall Response (BOR)**

Best Overall Response	Criteria
Complete Response (CR)	CR observed in consecutive assessments $\geq$ 4 weeks apart per RANO
Partial Response (PR)	PR observed in consecutive assessments $\geq$ 4 weeks apart per RANO
Stable Disease (SD) a	SD observed and does not qualify for CR or PR or Suspected PD followed with histologic results not confirming PD, and no CR PR, or SD observed
Not Evaluable (NE)	Insufficient data to determine disease progression or response
Progressive Disease (PD)	No CR, PR, or SD prior to PD

aTo qualify for SD there must be a minimum on-treatment period of 4 weeks.

For purposes of this study, the minimum duration between baseline (start of treatment) and first on-study scan in order to determine best objective response (BOR) of SD is 4 weeks. If the minimum time is not met when SD is otherwise the best time point response, the subject's best response will depend on the subsequent assessments. For example, a subject who has SD at a time point  $<$  4 weeks and PD at a second assessment, will have a best response of PD.

Participants with non-measurable disease at baseline only cannot have a complete or partial response, but their disease status will be assessed (SD or PD) at each tumor assessment, and they will be included in analysis of PFS and OS. Participants who have undergone surgical resection or biopsy at the time of their recurrence of meningioma and have as a result of that procedure non-measurable disease at their baseline MRI (lesions  $<$  10 mm x 10 mm on contrast enhancing MRI) will be followed for progression. If upon subsequent contrast-enhancing MRI, there are no significant signs of progression and the participant is clinically stable, the radiologic assessment will be categorized as SD.

Subjects with a complete or partial response must have that response sustained for 4 weeks. Subjects who do not qualify for complete response, partial response, or confirmed progression will be considered as stable disease for the protocol BOR analysis.

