may be exploited for immune based attack.(43-45) Sixth, immunosuppression, both systemically and in the tumor microenvironment, is a key feature associated with the pathogenicity of malignant primary CNS tumors including malignant glioma as well as meningioma.(46) Finally, meningiomas have better access to the systemic immune system than tumors arising in the brain parenchyma such as gliomas because meningiomas arise external to the blood brain barrier and are thus not restricted by endothelial cell tight junctions that can limit immune cell and large molecule penetration. Meningiomas are also directly exposed to the cerebrospinal fluid space that drains into the venous circulation, thereby facilitating tumor antigen presentation to cervical lymph nodes.

This study is being amended to add a second cohort (Cohort 2) which will build on the clinical experience acquired from the treatment of patients on Cohort 1 who were treated with nivolumab monotherapy following progression after prior surgery and radiation. For patients treated on Cohort 1, we observed that nivolumab monotherapy was well tolerated and no unexpected toxicities were observed. In addition, we noted that nivolumab monotherapy was associated with modest therapeutic benefit; specifically, one particularly heavily pretreated patient who had extensive tumor burden at study enrollment achieved a dramatic near complete response while 20-25% of patients achieved stable disease ([name], personal communication). To build on these encouraging yet modest results, we plan to add a second cohort of patients who will receive radiation therapy combined with immune checkpoint therapy consisting of anti-PD-1 (nivolumab) plus anti-CTLA-4 (ipilimumab).

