**Table 11.2-2 Summary of the RANO Response Criteria**

	CR	PR	SD	PD#
T1-Gd +	None	≥50% decrease	<50% decrease- <25% increase	≥25% increase*
T2/FLAIR	Stable or decrease	Stable or decrease	NA	NA
New Lesion	None	None	None	Present*
Corticosteroids	None	Stable or decrease	Stable or decrease	Stable or increasing
Clinical Status	Stable or increase	Stable or increase	Stable or increase	Decrease*
Requirement for Response	All	All	All	Any*

CR=complete response; PR=partial response; SD=stable disease; PD=progressive disease;  
NA= not applicable

#: Progression occurs when any of the criteria with \* is present

Increase in corticosteroids alone will not be taken into account in determining progression in the absence of persistent clinical deterioration

Of note, patients who require increased corticosteroids within two weeks of MRI assessment (relative to the dose taken at the time of the prior assessment) cannot be classified as CR, PR or SD and should be classified as non-evaluable at that time point. Conversely, patients who decrease corticosteroids within two weeks of MRI assessment (relative to the dose taken at the time of the prior assessment) cannot be classified as PD and should be classified as non-evaluable.

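### The last sentence of Section 11.5 turns every subject without CR, PR or confirmed progression into stable disease, against Table 11.5-1; only the descriptive best-response distribution is affected

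*Combined protocol and SAP*

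**What the plan says.** Section 11.5 (Best Objective Response) applies the criteria of Table 11.5-1 to the response assessments available for a subject. The Table has five categories.

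- NE: "Insufficient data to determine disease progression or response".
- PD: "No CR, PR, or SD prior to PD". The row does not mention confirmation.
- SD: either SD was observed and the subject does not reach CR or PR, or PD was suspected, histology did not bear it out, and no CR, PR or SD was seen. The footnote adds: "To qualify for SD there must be a minimum on-treatment period of 4 weeks".
- CR and PR: each must be seen in consecutive assessments at least 4 weeks apart.

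The text below the Table explains that when SD is seen too early, "the subject's best response will depend on the subsequent assessments". Its worked example is a subject with SD before 4 weeks who, with "PD at a second assessment, will have a best response of PD". The section's final sentence is then: "Subjects who do not qualify for complete response, partial response, or confirmed progression will be considered as stable disease for the protocol BOR analysis".

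Four other places bear on this.

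- Table 11.2-1 counts a failure to return through death or deterioration as PD.
- The note under Table 11.2-2 says that a scan taken within two weeks of a steroid increase "cannot be classified as CR, PR or SD and should be classified as non-evaluable at that time point". After a steroid decrease, a scan cannot be PD and is likewise non-evaluable.
- Section 11.4 asks for a confirming scan 12 weeks after a first radiologic PD within six months of starting therapy. It waives this for later progression. It treats neurologic decline during the wait as treatment failure, with progression back-dated.
- Section 14 states that no separate SAP will be issued.

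**The concern.** The final sentence has no exception for NE, no 4-week condition, and a requirement for confirmed progression that the Table's PD row does not contain. Two analysts working from the same data could therefore produce different BOR tables, each with support in Section 11.5. With no separate SAP, nothing settles which is right.

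The error runs in one direction. Subjects for whom there is no evidence of disease control, or whose only evidence is of progression, would be counted as SD. SD is not a neutral label in this protocol: Section 2.4 reports that "20-25% of patients achieved stable disease" in Cohort 1, beside one near-complete response, among the results that motivate Cohort 2. A reader may well take a reported SD proportion as a sign of activity.

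**Working it through.** **The plan's own figures.** No figure in the protocol depends on this rule, so there is none to reproduce. The check sets the two rules side by side and then counts.

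**Comparison by type of subject.**

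| Subject | Table 11.5-1 and its text | Final sentence, read literally |
|---|---|---|
| No post-baseline assessment, left for a reason other than death or deterioration | NE | SD |
| Every assessment non-evaluable because of steroid changes | NE | SD |
| Only an SD scan before 4 weeks, nothing later | Not SD; data insufficient, so NE | SD |
| First PD, no earlier CR, PR or SD, no later scan or histology refuting it | PD | SD |
| Suspected PD not confirmed by histology, no other finding | SD | SD |
| PD after six months, with evaluable SD scans before it | SD | SD |

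Only the first four rows differ. Subjects who fail to return through death or deterioration are left out of the differing group. Table 11.2-1 already makes them PD, and its confirmation step concerns radiographic progression.

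**How often the rows can arise, from the protocol's schedule.**

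- Scans are every 8 weeks, plus or minus 1 week, so the first falls at weeks 7 to 9. A scan before week 4 is off schedule, and the third row should be rare.
- Steroid non-evaluability attaches to a time point. The second row needs every assessment of that subject to be affected.
- Progression after six months usually follows scans near weeks 8, 16 and 24 that did not show PD. The waiver of confirmation there adds few cases.
- A first PD at week 8 would be confirmed at about week 8 + 12 = 20. Some such subjects may decline or leave before then. The fourth row is therefore foreseeable, as is the first: Section 14.1.2.2 provides for subjects who leave before the 8-week scan.

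**Size.** Let N be the cohort size, 25 (Section 14.1.4), and k the number of subjects in the first four rows. Then

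SD rate (final sentence) − SD rate (Table) = k/N, which is never negative.

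At N = 25 each subject adds 1/25 = 4 percentage points. The documents give no k. The starting counts below are also assumptions, chosen because 5/25 = 20% and 6/25 = 24% lie in the range that Section 2.4 mentions.

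| k (assumed) | From 5/25 | From 6/25 |
|---|---|---|
| 0 | 20% | 24% |
| 1 | 24% | 28% |
| 2 | 28% | 32% |
| 3 | 32% | 36% |
| 4 | 36% | 40% |
| 5 | 40% | 44% |

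**What does not move.** ORR counts confirmed CR or PR over response-evaluable subjects (Section 14.1.2.2). SD, NE and PD are all non-responders, and early leavers already stay in the denominator, so moving k subjects among these categories changes neither part of the fraction. PFS-6, PFS and OS are defined without BOR. The final threshold (at least 10 of 25 progression-free at six months) and the interim rule (at least 3 of 10) do not use it either.

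**The case against.** The best defence is contextual. The sentence follows directly on the requirement that CR and PR be sustained for 4 weeks. In that position it may be meant only to say where an unsustained response, or a PD later shown to be pseudoprogression, should go among subjects who have assessments. Section 11.5 has by then named the Table as the governing rule, so the NE row is not plainly abolished. The iRANO approach used here also treats a first radiologic PD as provisional. The affected group is small for the reasons shown in the working, and no named endpoint uses the SD rate.

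Much of this stands, and it limits the weight of the point. It does not remove the contradiction. The sentence does not restrict itself to subjects with assessments, and it declares that it governs the protocol's BOR analysis. Nor does the protocol treat the absence of a confirming scan as evidence against progression: Section 11.4 counts neurologic decline during the waiting period as failure, and the worked example in Section 11.5 ends in PD without confirmation.

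A reader might go further and infer that the Cohort 1 SD figure in Section 2.4 was inflated by this rule. The documents do not support that. The figure is a preliminary personal communication, and nothing shows how those subjects were classified. A reader might also infer that every subject without a post-baseline scan becomes SD; Table 11.2-1 already makes death and deterioration PD.

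**Conclusion.** Section 11.5 is wrong as written. Its last sentence and Table 11.5-1 cannot both be applied, and following the sentence assigns some subjects a BOR category that their data do not support, always towards SD. The consequence is confined to the descriptive BOR and SD distribution: k/25, or 4 percentage points per affected subject, for an unknown k that may be zero. This rests on a literal reading of the sentence and a denominator of 25.

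Any particular inflated SD rate, such as 24% becoming 40% with four affected subjects, is an illustration and not a finding. The stronger inference, that the trial's efficacy conclusions are biased, fails because no primary or secondary efficacy endpoint and no decision rule depends on the SD rate.

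**What to change.** Delete the sentence so that Table 11.5-1 governs. Alternatively, restrict it to subjects with at least one evaluable non-PD assessment at 4 weeks or later, for example a CR or PR that was not sustained. In either case, state the following.

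- Subjects with no evaluable assessment and no PD are NE and are reported in a separate row, with the denominator given.
- PD with no earlier CR, PR or SD, and with no later scan or histology refuting it, is PD, as in the Table's PD row.
- Suspected PD that histology does not confirm keeps the Table's route to SD.
- Where a follow-up scan after suspected PD shows SD, PR or CR, that scan determines the category.

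This changes a few lines of analysis text. It alters no assessment, no subject's treatment and no endpoint. The only cost is that the reported SD rate may be slightly less favourable.

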## 11.6 Neurologic Assessment in Neuro-Oncology (NANO)

Neurologic functioning will be evaluated using the overall score of The Neurologic Assessment in Neuro-Oncology (NANO) scale (Appendix F) which will be administered by the investigator at the study.

CONFIDENTIAL

This document is confidential. Do not disclose or use except as authorized.

The NANO scale is an objective, quick, user-friendly and quantifiable evaluation of nine major domains for subjects with brain tumors. The domains include: gait, strength, ataxia, sensation, visual field, facial strength, language, level of consciousness, behavior and overall. Each domain is rated on a scale of 0 to 3 where 0 represents normal and 3 represents the worst severity. A given domain should be scored non-evaluable if it cannot be accurately assessed due to pre-existing conditions, co-morbid events and/or concurrent medications. The evaluation is based on direct observation/testing performed during routine office visits. The NANO scale will be completed by the investigator or designated study physician prior to dosing Day 1 Week 1 (baseline) and then with each MRI (but must be completed prior to the review of the MRI scan results).

## **12. DATA REPORTING / REGULATORY REQUIREMENTS**

Adverse event lists, guidelines, and instructions for AE reporting can be found in Section 7.0 (Adverse Events: List and Reporting Requirements).

### **12.1 Data Reporting**

#### **12.1.1 Method**

The Office of Data Quality (ODQ) will collect, manage, and perform quality checks on the data for this study.

#### **12.1.2 Responsibility for Data Submission**

Investigative sites are responsible for submitting data and/or data forms to the ODQ in accordance with DF/HCC policies.

### **12.2 Data Safety Monitoring**

The DF/HCC Data and Safety Monitoring Committee (DSMC) will review and monitor toxicity and accrual data from this study. The committee is composed of medical oncologists, research nurses, pharmacists and biostatisticians with direct experience in cancer clinical research. Information that raises any questions about participant safety will be addressed with the Overall PI and study team.

The DSMC will review each protocol up to four times a year with the frequency determined by the outcome of previous reviews. Information to be provided to the committee may include: up-to-date participant accrual; current dose level information; DLT information; all grade 2 or higher unexpected adverse events that have been reported across all sites; summary of all deaths occurring with 30 days of intervention for Phase I or II protocols; for gene therapy protocols, summary of all deaths while being treated and during active follow-up; any response information; audit results, and a summary provided by the study team. Other information (e.g. scans, laboratory values) will be provided upon request.

### **12.3 Monitoring**

The quality control process for a clinical trial requires verification of protocol compliance and data

CONFIDENTIAL

This document is confidential. Do not disclose or use except as authorized.

accuracy. The Coordinating Center, with the aid of the ODQ, provides quality control oversight for the protocol.

Involvement in this study as a participating investigator implies acceptance of planned study monitoring, as well as potential audits or inspections, including both on-site and remote source data verification, by representatives designated by the DF/HCC Overall Principal Investigator (or Protocol Chair). The purpose of these reviews is to examine study-related activities and documents to determine whether these activities were conducted and data were recorded, analyzed, and accurately reported in accordance with the protocol, institutional policy, Good Clinical Practice (GCP), the Code of Federal Regulations (CFR), and any additional applicable regulatory requirements.

The Participating Institutions may be required to submit participant source documents to the Coordinating Center for monitoring. Participating Institution may also be subject to on-site monitoring conducted by the Coordinating Center.

Data will be monitored for timeliness of submission, completeness, and adherence to protocol requirements. Monitoring will begin at the time of participant registration and will continue during protocol performance and completion.

## **13. REGULATORY CONSIDERATIONS**

### **13.1 Protocol Review and Amendments**

This protocol, the proposed informed consent and all forms of participant information related to the study (e.g., advertisements used to recruit patients) and any other necessary documents must be submitted, reviewed and approved by a properly constituted IRB governing each study location.

Any changes made to the protocol must be submitted as amendments and must be approved by the IRB prior to implementation. Any changes in study conduct must be reported to the IRB. The DF/HCC Overall Principal Investigator (or a representative) will disseminate protocol amendment information to all participating investigator teams.

All decisions of the IRB concerning the conduct of the study must be made in writing.

